The research group of [name]. [name] of the Department of Oto-rhino-laryngology of the University Hospitals Leuven has more than six years of clinical experience with capsaicin (Figure 2), in treatment of patients with IR who do not respond well to the available treatment (i.e. intranasal corticosteroids).

[figure not shown]

Figure 2: Structural formula of capsaicin

In a very recent academic proof-of-concept study, major therapeutic effects have been shown on nasal symptoms and reduction of NHR in 14 patients with IR. That fact that confirms the work of several former investigators and a numerous amount of studies in which the therapeutic effect of capsaicin was already proven (9) (10) (11) (12) (13).

E. TRP channels

Since decades capsaicin (8-methyl-N-vanillyl-6-nonenamide), the natural extract of red, hot chili pepper, is used as an analgesic in topical preparations (14) (15).

Prolonged exposure to capsaicin makes the afferent nerves insensitive not only to the pungent substance but also to other noxious stimuli. The process of defunctionalization of nociceptor fibers is the mechanism behind its analgesic properties (14) and its therapeutic properties are due to the effect of capsaicin on the transient receptor potential V1 (TRPV1) on the sensory C-fibers in the nasal mucosa (16).

Activation of these peripheral sensory nerve endings can trigger the TRP channel family - a family of chemoreceptors present in the airway lining.

Currently, a lot of research is devoted to these channels because there is a strong conviction that disturbances in afferent sensory mechanisms are very important in the pathogenesis of functional problems (17).

Members of the mammalian TRP family that are of specific importance for our research are TRPA1 (Ankyrin 1), TRPM8 (Melastatin 8) and TRPV1 (Vanilloid 1).

TRPA1 is very commonly expressed in the nasal mucosa and is functioning as a major irritant detector. Therefore it is believed to play a crucial role in occupational rhinitis.

The TRPM8 channel itself is activated by cold temperatures (as well as TRPA1) and TRPM8 activation leads to a cold sensation. Its function is not yet completely understood.

Interestingly, approximately nine months after capsaicin treatment, symptoms tend to recur. The underlying mechanism is still uncertain, but is currently being investigated by the fundamental research team of [name]. [name].

Objectives

A. Aims

Our primary aim is:

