- To evaluate if two novel treatment modalities (explained more briefly on page 9 in paragraph 'Study Onset' of chapter 'Methodology') show non-inferiority on subjective evaluations (symptom score on a Visual Analogue Scale (VAS), Therapeutic Response Evaluation (TRE) and Rhinitis Quality of Life Questionnaire (RQLQ)) compared to the current treatment modality of capsaicin nasal treatment in patients with IR. The gathered data of this single center trial can be used to guide the decision on the set-up and the design of a larger multi-center trial being powered to prove non-inferiority.

Our secondary aims are:

- To evaluate if the two novel treatment modalities show non-inferiority compared to the current treatment modality of capsaicin nasal treatment in patients with IR on objective evaluations (Peak Nasal Inspiratory Flow (PNIF) measurements before and after CDA challenge).
- To evaluate the occurrence of adverse events at week 4, week 12 and week 26 and recurrence of symptoms and NHR at week 26 in the different treatment groups.

B. Hypothesis

Non-inferiority in efficacy of the two novel treatment regimes i.e. capsaicin nasal spray 0,01mM (2puffs/nostril/day) during 4 weeks and capsaicin nasal spray 0,001mM (2puffs/nostril/day) during 4 weeks compared to the current treatment of capsaicin nasal spray 0,1mM (5/day administered on a single day) with regard to the scores on week 4 (taking into account the baseline level).

C. Outcome

- VAS for major nasal symptom at week 4, week 12 and week 26. The region of equivalence is defined as a difference in VAS of less than 1.
- VAS for total and individual nasal symptoms at week 4, week 12 and week 26. The region of equivalence is defined as a difference in VAS of less than 1.
- TRE (based on a scale from 1 to 5) at week 4, week 12 and week 26. The region of equivalence is defined as a difference in percentage for patients of less than 10% in all different TRE scoring groups.

- NHR (objectively measured by PNIF before and after CDA challenge) in all treatment modalities at week 4, week 12 and week 26. The region of equivalence is defined as a drop in PNIF of less than 10%.
- Appearance of adverse events at week 4, week 12 and week 26.
- Recurrence of symptoms (based on a scale of 1 to 5) at week 26.

Study design

A. Type of study

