Functional problems that are most troublesome to adults with rhinitis will be measured by the RQLQ by 28 questions in 7 domains (activity limitation, sleep problems, nose symptoms, eye symptoms, non-nose/eye symptoms, practical problems and emotional function). There are three 'patient-specific' questions in the activity domain, which allow patients to select three activities in which they are most limited by their rhinitis. Patients recall how bothered they have been by their rhinitis during the previous week and to respond to each question on a 7-point scale (0 = not impaired at all and 6 = severely impaired). The overall RQLQ score is the mean of all 28 responses and the individual domain scores are the means of the items in those domains. The RQLQ has excellent measurement properties and has been used extensively throughout the world both in clinical practice and clinical trials. The validation studies have shown that these properties are very similar to

those found for the Asthma Quality of Life Questionnaire (21). Patients will be asked to score RQLQ before treatment and at week 4, 12 and 26.

- Adherence evaluation:

Patients will be asked to bring their nasal spray with them on follow up visit 2 at week 4. Weighing the residual fluid on day 28 will objectively check adherence.

All patients will be asked to write down their symptoms, adverse events and degree of sensitization/desensitization in a dairy (see addendum). The diary will be handed over to them at the day of the treatment.

- Therapeutic Response Evaluation (TRE):

TRE will be measured on a 1 to 5 scale.

- 5 klachten zijn volledig verdwenen = klachtnvrij
- 4 klachten zijn bijna volledig verdwenen
- 3 klachten zijn verminderd, doch nog aanwezig
- 2 klachten zijn licht verminderd, doch nog sterk aanwezig
- 1 klachten zijn onveranderd ten opzichte van vóór de behandeling

Patients will be asked to score their symptom relief on week 4, week 12 and week 26.

- Evaluation of recurrence of symptoms:

The recurrence of symptoms will be measured on a 1 to 5 scale.

- 5 klachten zijn volledig terug aanwezig
- 4 klachten zijn voor een aanzienlijk deel terug aanwezig
- 3 klachten zijn nog steeds duidelijk verminderd
- 2 klachten zijn licht verminderd, doch beginnen terug te keren
- 1 klachten zijn nog steeds volledig verdwenen

Patients will be asked to score their recurrence of symptoms at week 26.

References

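### The week 26 recurrence score cannot be separated from initial non-response, and week 26 can show only early recurrence

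*Combined protocol and SAP*

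**What the plan says.** **Aim and outcome.** A secondary aim (Objectives, A. Aims) is to evaluate "recurrence of symptoms and NHR at week 26 in the different treatment groups". The outcome list (Objectives, C. Outcome) has "Recurrence of symptoms (based on a scale of 1 to 5) at week 26", with no region of equivalence attached. The groups are the four arms of 30 in Methodology, A. Study onset, one of which is placebo/placebo.

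**The item.** Methodology, I. Variables says "Patients will be asked to score their recurrence of symptoms at week 26". Nothing limits this to patients who first improved. The scale (in Dutch) runs from "1 klachten zijn nog steeds volledig verdwenen" (still completely gone) to "5 klachten zijn volledig terug aanwezig" (fully back). The levels between describe symptoms that are reduced, that are starting to return, or that have largely returned.

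**The response scale.** TRE is a separate 1 to 5 scale, scored at weeks 4, 12 and 26. Its lowest level is "1 klachten zijn onveranderd ten opzichte van vóór de behandeling", that is, unchanged from before treatment. The recurrence scale has no such level.

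**Analysis.** Methodology, D. Statistics gives models for VAS, RQLQ, the drop in PNIF, and the proportion with TRE 5. It gives none for the recurrence score and does not relate that score to earlier TRE.

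**Timing.** The background (E. TRP channels) says that "approximately nine months after capsaicin treatment, symptoms tend to recur".

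**The concern.** Recurrence has meaning only after relief. If patients who never had relief answer the item, their answers enter the group comparison as though relief had been gained and lost. The comparison then reflects how many patients responded at first as well as how long the response lasted, and nothing in the plan separates the two.

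The direction is predictable: the arm with the lower initial response looks worse on durability. Initial response is what this trial compares between regimens, and one arm is placebo. The results are also meant to guide the design of a larger multi-centre trial, so a wrong impression of durability could be carried forward.

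Timing adds a second limit. If loss of effect is usually seen at around nine months, similar scores at week 26 do not show that two regimens last equally long.

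**Working it through.** **1. What a never-relieved patient can answer.** Take a patient with TRE 1 at weeks 4 and 12. Levels 1 to 3 of the recurrence item describe symptoms that are gone or reduced, which is untrue for this patient. Levels 4 and 5 describe symptoms that have come back. Level 5 is the nearest description of the current state, although nothing has come back.

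**2. Effect on a comparison of two arms.** Let r be the proportion who respond, q the proportion of responders fully relapsed by week 26 (the same in both arms), and s the proportion of never-responders who choose 5. Then

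P(score 5) = (1 − r)s + rq, and the difference between arms A and B is (rA − rB)(s − q).

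The true difference in relapse among responders is zero. The apparent difference is positive whenever rA exceeds rB and s exceeds q. The documents give none of these rates, so all values below are assumptions, with s = 1.

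- Arm A, r = 0.80, q = 0.20: 0.20 + 0.80 × 0.20 = 0.36.
- Arm B, r = 0.50, q = 0.20: 0.50 + 0.50 × 0.20 = 0.60.
- Difference: 0.30 × 0.80 = 0.24.

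Other assumed rates. The last column is the chance of a two-sided p < 0.05 with 30 per arm, shown only to convey size, since the plan specifies no such test:

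| q | Response, A vs B | Scored as back, A vs B | Difference | Chance of p < 0.05 |
|---|---|---|---|---|
| 0.19 | 80% vs 20% | 35% vs 84% | 0.49 | 98% |
| 0.19 | 70% vs 30% | 43% vs 76% | 0.32 | 74% |
| 0.19 | 60% vs 40% | 51% vs 68% | 0.16 | 24% |
| 0.37 | 80% vs 20% | 50% vs 87% | 0.38 | 90% |
| 0.37 | 70% vs 30% | 56% vs 81% | 0.25 | 56% |
| 0.37 | 60% vs 40% | 62% vs 75% | 0.13 | 18% |

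**3. Timing.** One month is 365.25/12/7 = 4.348 weeks, so nine months is 39.1 weeks. Week 26 falls 39.1 − 26 = 13.1 weeks earlier, at 6.0 months from the treatment day.

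**4. How much of the score would come from non-response?** Assume a Weibull time to recurrence with a median of nine months. Then q = 1 − exp(−ln 2 × (26/39.13)^k), which is 0.37, 0.26, 0.18 and 0.09 for shape k = 1, 2, 3 and 5. With s = 1, the share of scores of 'back' that come from never-responders in one arm is (1 − r)/[(1 − r) + rq]. Ranges over the four shapes:

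| Response on capsaicin | Capsaicin arms only | All four arms (30% placebo response) |
|---|---|---|
| 50% | 73–92% | 77–93% |
| 70% | 54–83% | 64–89% |
| 80% | 40–74% | 57–85% |
| 90% | 23–56% | 47–80% |

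Within one arm, never-responders are the majority only if response is below 1/(1 + q), which is 73% for k = 1 and 92% for k = 5.

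**The case against.** **Other outcomes already show durability.** VAS, RQLQ and TRE are collected through week 26. The planned models compare VAS, RQLQ and the proportion with TRE 5 over time in all four groups, with intervals at specific time points for the differences from the linear models. Loss of effect would be visible there without any responder definition. This stands, and it limits the harm to one secondary item.

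**The trial is a descriptive pilot.** The plan sets no margin for recurrence, claims no equal duration, names week 26 in the aim, and states no rule for counting a score of 5 as a recurrence. All true. But a descriptive table of this score by group would still mix two different things, and the reader could not tell how much of each.

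**TRE would allow the split afterwards.** It would, but a response threshold chosen with the data in hand is open to selection.

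**Stronger readings.** A reader might infer that the score would mostly measure non-response. The documents give no response rates and no distribution of recurrence times, and under the assumptions above the share falls below half in the capsaicin arms when response is high and recurrence times are widely spread. A reader might also infer that true recurrence must be rare by week 26, so that the visit tells nothing. The nine-month remark is approximate and describes earlier capsaicin use. The documents give no recurrence time for the two new regimens, so early loss of effect there is an open question that week 26 can help answer.

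**Conclusion.** The point holds as a defect of definition and analysis. As written, the recurrence score at week 26 confounds loss of response with absence of response, and the bias runs against the arm with the lower initial response. Its size cannot be fixed from the documents: 24 percentage points in the 80% versus 50% example, and 13 to 49 points over the tabulated assumptions. All of these assume equal relapse among responders and that never-responders choose the top of the scale.

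Week 26 lies about 13 weeks before the protocol's own approximate time of recurrence. It can reveal early recurrence but cannot by itself support a statement that the regimens last equally long.

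The primary aim is not affected. For a secondary outcome of a pilot this is a modest point, worth acting on because the correction is specific and cheap.

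**What to change.** 1. Add an answer to the recurrence item for patients whose symptoms never improved.
2. Pre-specify three categories from TRE, with one threshold at all visits. For example: *never responded* (TRE below 3 at weeks 4 and 12), *responded and maintained* (TRE of 3 or more at week 4 or 12, and again at week 26), *responded and lost* (TRE of 3 or more at week 4 or 12, but below 3 at week 26). Repeat with TRE 5, the cut-off already used in the Statistics section, as a sensitivity analysis.
3. Compare *responded and maintained* between groups among all randomised patients, and state how a missing week 26 TRE is handled (the protocol allows for 10% dropout, or 0.10 × 30 = 3 per arm).
4. Report the recurrence score in prior responders descriptively only, with the denominator for each arm.
5. State that week 26 assesses early recurrence and that no conclusion on equal duration rests on it.

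**Cost.** One extra answer on the form, one derived variable and a few sentences of text; no new visit, and no contact after month nine is needed. The threshold is a convention. The description in responders rests on fewer patients and is not protected by randomisation, because it conditions on an outcome after treatment; this is why the main comparison should keep all randomised patients.

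While the item is being edited, check the order of levels 2 and 3: level 3 (still clearly reduced) reads as the milder state than level 2 (slightly reduced and starting to return).
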